#### **Non-measurable disease**

Non-measurable disease includes lesions too small to be considered measurable (including nodes with short axis between 10 and 14.9 mm) and truly non-measurable disease such as pleural or pericardial effusions, ascites, inflammatory breast disease, leptomeningeal disease, lymphangitic involvement of skin or lung, clinical lesions that cannot be accurately measured with calipers, abdominal masses identified by physical exam that are not measurable by reproducible imaging techniques.

- Bone disease (based on PCWG3 criteria): Bone disease is defined as present or absent and will be followed as non-target lesions.
- Previous local treatment: A previously irradiated lesion (or lesion patiented to other local treatment) is non-measurable unless it has progressed since completion of treatment.

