### **New Lesions**

The appearance of any new unequivocal malignant lesion indicates PD. If a new lesion is equivocal, for example due to its small size, continued assessment will clarify the etiology. If repeat assessments confirm the lesion, then progression should be recorded on the date of the initial assessment. A lesion identified in an area not previously scanned will be considered a new lesion.

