## Appendix 5. Guidelines for Evaluation of Bone Scans

*Based on Prostate Cancer Working Group 3.*

An international expert committee of prostate cancer clinical investigators (the Prostate Cancer Clinical Trials Working Group 3 [PCWG3]) was reconvened and expanded and met in 2012-2015 to formulate updated criteria on the basis of emerging trial data and validation studies of the Prostate Cancer Clinical Trials Working Group 2 recommendations.

Given the frequency of bone involvement in patients with progressive, castration-resistant disease, the decreased emphasis of early changes in PSA, and the increased availability of cytostatic agents, reliable methods to assess changes in bone are of increasing importance. PCWG3 recognizes that standards for using MRI and PET to assess bone metastases are under active investigation, so only radionuclide bone scans are considered here. PCWG3 also recognizes that there are no validated criteria for response on radionuclide bone scan.

For control/relieve/eliminate end points, the PCWG3 recommends that post-treatment changes be recorded “no new lesions,” “new lesions” or “resolved bone lesion.” However, progression at the first scheduled assessment should be confirmed on a second scan performed 6 or more weeks later, in the absence of clearly worsening disease or disease-related symptoms. In the event of visible lesions disappearing, this should also be confirmed at the next scheduled assessment.

For prevent/delay end points, progressing disease on bone scan is considered when at least two new lesions relative to the first post-treatment scan is confirmed on a subsequent scan. PCWG3 does not recommend performing a follow-up bone scan before 12 weeks of treatment unless clinically indicated. At the first 12-week reassessment, defining disease progression requires a confirmatory scan (which shows additional new lesions compared with the first follow-up scan) performed 6 or more weeks later, because lesions visible at the first 12-week assessment may represent disease that was not detected on the pretreatment scan. When further progression is documented on the confirmatory scan, the date of progression recorded for the trial, is the date of the first scan that shows the change.

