Selected ad-hoc efficacy analyses (eg, ORR and radiographic PFS) combining participants from Cohorts 7A and 3B may be conducted, as participants in those two cohorts have identical or similar eligibility criteria for study entry and are scheduled to receive the same regimen.

Swimmer plots may be used to display duration of treatment and tumor response at each applicable time point. Waterfall plot for individual tumor size percent change from baseline, and spider plot for individual tumor size percent change from baseline over time may be presented. These plots, if generated, will be presented for RECIST 1.1 and irRECIST separately.

For the rPFS analysis in Part B, the Kaplan-Meier analysis may be performed if deemed necessary. If the Kaplan-Meier analysis is performed for radiographic progression-free survival, an event is defined as the first occurrence of “PD” status by investigator, or death, or a PCWG3 defined bone disease progression, whichever comes first, under RECIST. Time zero for all time-to-event analyses will be defined as the first vaccination on Cycle 1 Day 1. This analysis may be performed for the combined cohorts 7A and 3B. CCI

For duration of response per RECIST and time to response (from the first vaccination date to the time of the first response, CR or PR) in Part B, descriptive statistics will be provided. Kaplan-Meier analysis may be performed if deemed necessary. These analyses may be performed for the combined cohorts 7A and 3B.

PSA kinetics

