The percentage of MDSCs will be assessed in pretreatment (Screening, Cycle 1 Day 1) and post treatment samples. MDSC levels will be presented per patient and per cohort by GMTs and GMFRs. Analyses of MDSC endpoints may include absolute and fold-change from baseline (pretreatment) by patient and % change and mean fold-change by cohort.

Bone scan assessment

Given the frequency of bone involvement in patients with progressive, castration-resistant disease, the decreased emphasis of early changes in PSA, and the increased availability of cytostatic agents, reliable methods to assess changes in bone are of increasing importance. PCWG3 recognizes that standards for using MRI and PET to assess bone metastases are under active investigation, so only radionuclide bone scans are considered here. PCWG3 also recognizes that there are no validated criteria for response on radionuclide bone scan.

[figure not shown]
For control/relieve/eliminate end points, the PCWG3 recommends that post-treatment changes be recorded simply as either “no new lesions” or “new lesions.” However, progression at the first scheduled assessment should be confirmed on a second scan performed 6 or more weeks later, in the absence of clearly worsening disease or disease-related symptoms. In the event of visible lesions disappearing, this should also be confirmed at the next scheduled assessment.

For prevent/delay end points, progressing disease on bone scan is considered when a minimum of two new lesions is observed. PCWG3 does not recommend performing a follow-up bone scan before 12 weeks of treatment unless clinically indicated. At the first 12-week reassessment, defining disease progression requires a confirmatory scan (which shows additional new lesions compared with the first follow-up scan) performed 6 or more weeks later, because lesions visible at the first 12-week assessment may represent disease that was not detected on the pretreatment scan. When further progression is documented on the confirmatory scan, the date of progression recorded for the trial, is the date of the first scan that shows the change.

Correlative analyses

Plots may be generated to display PSA kinetics vs. PSA antibodies (serology: Luminex assay). Similar plots may be generated to evaluate individual patient trends on MDSC, CTC and T-cell response.

CCI

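### After the first reassessment, SAP 8.1.3 lets two unconfirmed new bone lesions count as progression (prevent/delay end points); protocol Appendix 5 requires confirmation on a later scan

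*SAP*

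**What the plan says.** SAP 8.1.3, under the bone scan assessment, has two paragraphs. For prevent/delay end points, "progressing disease on bone scan is considered when a minimum of two new lesions is observed". That paragraph then keeps one confirmation step: "At the first 12-week reassessment, defining disease progression requires a confirmatory scan", to be done 6 or more weeks later and to show further new lesions. For control/relieve/eliminate end points, the SAP says that "progression at the first scheduled assessment should be confirmed on a second scan performed 6 or more weeks later".

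Protocol Appendix 5 has the same two paragraphs. Its control/relieve/eliminate confirmation rule matches the SAP. Its prevent/delay sentence does not: it requires that "at least two new lesions relative to the first post-treatment scan is confirmed on a subsequent scan". The text on the 12-week reassessment that follows is the same in both documents.

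Two other places in the protocol ask for confirmed progression. The tumor assessment footnote to the Schedule of Activities asks, for progression in general, for two consecutive timepoints at least 4 to 6 weeks apart. Section 6.4.1, on withdrawal from treatment, sets at least 6 weeks for bone scan progression. Both except rapid clinical deterioration.

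Bone progression enters rPFS in SAP 8.1.3. The event is investigator PD, or death, "or a PCWG3 defined bone disease progression, whichever comes first, under RECIST".

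**The concern.** The SAP sentence leaves out two things that Appendix 5 has: the reference scan against which lesions are new, and confirmation on a later scan. Once the first reassessment has passed, a pair of new lesions that the next scan does not confirm is bone progression under one document and not under the other.

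rPFS is a Part B secondary endpoint for Cohort 3B (protocol 2.3), and SAP 4.3 ranks it directly behind objective response rate in that cohort. Two programmers, one working from the SAP sentence and one from Appendix 5, could derive different event status for the same patient. At stake is agreement between the documents on an event definition in a cohort of 18.

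**Working it through.** The plan gives no figure of its own on this point. The check sets the two rules side by side on the scan schedule.

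**Inputs**
- Imaging every 8 weeks ± 5 days, the first 8 weeks after Cycle 1 Day 1; bone scans only when indicated (Schedule of Activities, tumor assessment footnote).
- Confirmation interval of 6 weeks or more, that is 42 days (SAP 8.1.3, Appendix 5).
- Cohort 3B: 18 patients (protocol 9.3, SAP 4.3).

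**Step 1: where the 12-week reassessment falls.** Scan windows in days after Cycle 1 Day 1 are 56k ± 5: 51–61 (Week 8), 107–117 (Week 16), 163–173 (Week 24). Week 12 is Day 84, which is 84 − 61 = 23 days after the first window closes and 107 − 84 = 23 days before the second opens. No scan is scheduled there, so two readings are possible:
- *Reading 1:* the reassessment is the first on-study bone scan. The SAP's comparison with the first follow-up scan leans this way.
- *Reading 2:* it is the Week 16 scan, the first after Week 12. The advice in the same paragraph against follow-up bone scans before 12 weeks leans this way.

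**Step 2: apply both prevent/delay rules.**

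| Bone scans | SAP, reading 1 | SAP, reading 2 | Appendix 5 |
|---|---|---|---|
| Clear Week 8; two new lesions Week 16; not confirmed Week 24 | Progression, Week 16 | None (confirmation required) | None |
| Clear Weeks 8 and 16; two new lesions Week 24; not confirmed Week 32 | Progression, Week 24 | Progression, Week 24 | None |

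The documents part from the second on-study bone scan on reading 1 and from Week 24 on reading 2. On neither reading do they agree throughout.

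**Step 3: confirmed lesions.** Both documents date confirmed progression to the first scan that shows the change. For confirmed lesions judged against the same reference scan, event and date are the same.

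**Step 4: can a routine scan supply the confirmation?** Shortest gap between consecutive scans: 163 − 117 = 46 days. Longest: 173 − 107 = 66 days. Both exceed 42, so the next 8-weekly scan is late enough.

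**Step 5: size.** With no earlier censoring, one event moves the Cohort 3B Kaplan-Meier curve by 1/18 = 5.6 percentage points; earlier censoring would make the step larger. The documents give no rate of unconfirmed findings, so the number of such patients, which may be zero, cannot be derived.

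**The case against.** The strongest objection is that the effect on rPFS is conditional. Neither document's visible text says which bone paragraph governs the rPFS component, and under the control/relieve/eliminate paragraph the confirmation rules agree. Redacted text follows the rPFS definition in SAP 8.1.3, protocol 7.4 is partly redacted, and SAP 10.3 leaves rPFS programming to a specification that is not among the documents and may restore confirmation. This stands. The missing link cannot be called an omission, and the effect on rPFS can only be stated with an *if*.

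Second, a patient with unconfirmed bone lesions may be an event anyway. Protocol Appendix 3 says "The appearance of any new unequivocal malignant lesion indicates PD", without confirmation, and investigator PD is itself an rPFS event. Against that, the same appendix says "Bone disease is defined as present or absent and will be followed as non-target lesions", on PCWG3 criteria. Whether new bone lesions alone enter by that route is not settled in the visible text, so zero net effect is possible.

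Third, protocol Section 9 lets the SAP modify non-primary plans. That is so, but SAP 8.1.3 does not say that it means to replace Appendix 5. The log entry for 8.1.3 mentions only added clarity and does not show when this sentence took its present form.

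Three stronger readings might be inferred, and the documents do not support them:
- *That the SAP drops confirmation altogether.* It keeps it at the first assessment in both paragraphs.
- *That lesions first seen at Week 16 and unconfirmed are certainly progression under the SAP.* This fails on reading 2.
- *That the reported rPFS will be wrong.* Nothing in the documents shows that any patient is affected.

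**Conclusion.** The two prevent/delay sentences contradict each other, and that does not depend on the reading chosen; only the scan at which the difference begins does. An effect on Cohort 3B rPFS rests on three assumptions: the prevent/delay paragraph governs the bone component, the programming specification follows the SAP sentence, and the patient is not already an event through investigator PD.

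The impact is small: zero or more patients at 5.6 points each. SAP 4.1 plans no hypothesis test, bone scans are done only when indicated, and for rPFS "the Kaplan-Meier analysis may be performed if deemed necessary". The point is worth correcting because the repair is one sentence, not because a conclusion is known to turn on it. It concerns the analysis event only, not decisions about treatment.

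**What to change.** In SAP 8.1.3, replace the prevent/delay sentence with the one in Appendix 5, including both the reference scan and confirmation on a subsequent scan; or keep the SAP sentence, declare it as a departure and justify it. Make the Analysis Programming Specification consistent with the choice.

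**Cost.** One SAP sentence and a consistency check of the specification. No protocol amendment is needed, and no added scans where 8-weekly bone scanning continues. The downside is that patients whose last scan shows unconfirmed lesions would not be bone events. An optional sensitivity analysis that counts unconfirmed lesions as events would show how much this matters.

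**Separate minor point, SAP 10.4.** For patients without a baseline assessment, the irPFS text counts a death up to the second planned tumor assessment as an event, while footnote a of Table 2 stops at 8 weeks. If planned assessments are counted from the first post-baseline one, the second is at 2 × 8 = Week 16 and the two conflict. Reconcile the footnote with the text; only patients without a baseline assessment are affected.

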8.1.5. Pharmacokinetics

Patients who receive the designated investigational product of interest and have at least one post-dose drug concentration measurement will be included in the PK data analysis.

The actual time of sample collection will be used in PK parameter calculation. In the event that the actual sampling time is not available, the nominal time may be used if there is no evidence that the actual sampling time deviates substantially from the nominal time.

8.1.5.1. Tremelimumab and PF-06801591 Pharmacokinetics

Presentation of Tremelimumab and PF-06801591 concentration-time data

The concentration-time data of tremelimumab and PF-06801591 will be presented as below:

- a listing of all concentrations by cohort, subject ID and nominal time for each compound. The concentration listings will also include the actual times. Deviations from the nominal time will be given in a separate listing for each compound.
- a summary of concentrations for each compound by cohort and nominal time, where the set of statistics will include n, mean, standard deviation, median, coefficient of

variation (cv), minimum, maximum and the number of concentrations above the lower limit of quantification.

- for the concentration-time data after the first dose median concentrations time plots (on both linear and semi-log scales) against nominal time postdose by cohort (all cohorts on the same plot per scale, based on the summary of concentrations by cohort and time postdose) for tremelimumab (for Cohorts 3A and 4A only) and PF-06801591 (for Cohorts 6A through 9A).

for the concentration-time data after the first dose mean concentrations time plots (on both linear and semi-log scales) against nominal time postdose by cohort (all cohorts on the same plot per scale, based on the summary of concentrations by cohort and time postdose) for tremelimumab (for Cohorts 3A and 4A only) and PF-06801591 (for Cohorts 6A through 9A).

For drug concentration summary statistics, median and mean plots by sampling time, the nominal PK sampling time will be used.

Calculation of tremelimumab PK parameters

For patients of Cohorts 3A and 4A, the concentration-time data of tremelimumab after the first dose will be analyzed individually by non-compartmental methods to determine the PK parameters. For patients of Cohorts 6A through 9A, the concentration time data of PF-06801591 after the first dose will be analyzed individually by non compartmental methods to determine the PK parameters. For each compound, the PK parameters to be estimated will include the maximum drug concentration (C_{max}), time to maximum drug concentration (T_{max}), and area under the concentration versus time curve (AUC) from time zero to the last quantifiable time point prior to the second tremelimumab or PF-06801591 dose (AUC_{last}), and if data permit, AUC from time zero extrapolated to infinity (AUC_{inf}), terminal elimination half-life ($t_{1/2}$), and apparent clearance (CL/F). In addition, the accumulation ratio (Rac) as calculated by the ratio of the trough concentration prior to the fifth tremelimumab or PF-06801591 dose (on Cycle 2 Day 1) to the concentration prior to the second tremelimumab or PF-06801591 dose (on Cycle 1, Day 29) will be determined individually if data permit.

PK parameters will be calculated using standard non-compartmental methods:

Parameter	Method of Determination
AUC _{last}	Linear/log trapezoidal method
AUC _{inf} ^a	AUC _{last} + (C _{last*} /k _{el}), where C _{last*} is the predicted concentration at the last quantifiable time point (T) estimated from the log-linear regression analysis, and k _{el} is the terminal phase rate constant calculated by a linear regression of the log-linear concentration-time curve. The terminal log-linear phase will be determined from a minimum of 3 concentration-time data points, and will be verified with the r ² value.
C _{max}	Observed directly from data
CL/F ^a	Dose/AUC _{inf}
t _{1/2} ^a	ln2/k _{el}
T _{max}	Observed directly from data

^a if data permit.

The PK parameters of each compound will be summarized as below:

[figure not shown]
Parameter	Summary statistics
AUClast, AUC _{inf} , C _{max} , and CL/F	N, arithmetic mean, median, cv%, standard deviation, minimum, maximum, geometric mean.
t _{1/2}	N, arithmetic mean, median, cv%, standard deviation, minimum, maximum.
T _{max}	N, median, minimum, maximum.

8.1.6. Tremelimumab and PF-06801591 Immunogenicity

For patients receiving tremelimumab, the percentage of subjects with positive ADA and neutralizing antibodies will be summarized by dosing cohort. For patients with positive ADA, the magnitude (titer), time of onset, and duration of ADA response will also be described, if data permit.

For patients receiving PF-06801591, the percentage of subjects with positive ADA and neutralizing antibodies will be summarized by dosing cohort. For patients with positive ADA, the magnitude (titer), time of onset, and duration of ADA response will also be described, if data permit.

CCI

CCI

10. APPENDICES

10.1. Appendix: Statistical Methods for Immunogenicity (serology)

Definitions:

Let x_i , $i=1, 2, n$, be the titer for subject i where n is the number of subjects. Then the geometric mean titer (GMT) is defined as follows

$$\text{GMT} = \exp[(1/n)\sum \log(x_i)],$$

where \log is the natural logarithm.

Within each vaccine group and for each antibody, geometric mean titers (GMTs) will be calculated. Each titer will be logarithmically transformed for analysis. Two (2)-sided, 80% confidence intervals will be constructed by back transformation of the confidence intervals for the mean of the logarithmically transformed assay results.

Let x_i , $i=1, 2, n$, be the titer for test group and let y_i , $i=1, 2, m$, be the titer for reference group. Then the geometric mean ratio (GMR) is defined as follows:

$$\text{GMR} = \exp[(1/n)\sum \log(x_i) - (1/m)\sum \log(y_i)].$$

Also for the GMRs, the confidence intervals will be constructed by back transformation of the confidence intervals for the mean difference of the logarithmically transformed assay results (*test* relative to *reference*).

Let x_i , $i=1, 2, n$, be the titer prior vaccination and let y_i , $i=1, 2, n$, be the titer post vaccination. Then the geometric mean fold rise (GMFR) is defined as follows:

$$\text{GMFR} = \exp[(1/n)\sum \log(y_i/x_i)].$$

For the geometric mean fold rise, the confidence intervals will be constructed by back transformation of the confidence intervals for the mean difference of the logarithmically transformed assay results (*post* to *prior*).

GMTs, GMRs and GMFR will be estimated by an ANCOVA model with natural log transformed anti-body titer as outcome variable, and treatment group as factor and baseline (in log scale) as covariates at each of the post-dose measurement. These analyses based on log-transformed data, the LSMEAN estimates and confidence interval will be back-transformed (exponentiated) and presented. The estimated treatment difference and corresponding confidence intervals from the model will also be back-transformed.

-For GMTs the variable of interest, that will be back transformed, is $\log(x_i)$

x_i , $i=1, 2, n$, be the titer for subject i

-For GMFRs the variable of interest, that will be back transformed, is $\log(y_i) - \log(x_i)$

x_i , $i=1, 2, n$, be the titer prior vaccination and let y_i , $i=1, 2, n$, be the titer post vaccination

Back-transformation of estimated difference in GMTs (with contrasts) is interpreted as GMR between treatment and placebo group.

In addition to the adjusted analysis for GMTs, GMRs and GMFRs between groups through analysis of covariance, unadjusted (crude) GMTs, GMRs and GMFRs will be calculated as a sensitivity analysis.

For GMTs, two (2)-sided, 80% confidence intervals will be constructed by back transformation of the confidence intervals for the mean of the logarithmically transformed assay results computed using the Student t distribution.

For the GMRs, the confidence intervals will be constructed by back transformation of the confidence intervals for the mean difference of the logarithmically transformed assay results (*test* relative to *reference*) computed using the Student t distribution.

For reporting purposes, 1 decimal place will be used for geometric mean titers (GMTs), and 2 decimal will be used for geometric mean ratios (GMFRs, GMRs).

